4.1.6. Extent of Exposure

The *extent of exposure* to study medication will be assessed by duration of treatment exposure, derived as:

$$\text{Duration of treatment exposure} = \text{Treatment end date} - \text{Treatment start date} + 1$$

4.2. Endpoint-Related Definitions

4.2.1. Study Eye and Fellow Eye

The study eye will be the eye that qualifies per eligibility criteria at Visit 2. If both eyes meet the eligibility criteria, the eye with the higher mean diurnal IOP at Visit 2 will be designated as the study eye. If both eyes meet the eligibility criteria and have the same mean diurnal IOP, the right eye will be designated as the study eye. The other eye will be the non-study eye, or fellow eye.

4.2.2. Baseline Score

The *baseline score* is the observed measurement at Visit 2 (Baseline). If a baseline score is missing, the last observed measurement or derived score prior to the first dose of study medication will be used to impute the baseline score.

4.2.3. Change and Percent Change from Baseline

The change and the percent change from baseline in a measure at a post-baseline visit will be derived as:

- Change = (Score at the Post-Baseline Visit) – (Baseline Score).
- Percent Change from Baseline = $100 \times \text{Change} / (\text{Baseline Score})$.

4.3. Efficacy-Related Definitions

4.3.1. Response Endpoint and Response Rate

Four IOP response endpoints ([Table 3](#)) will be evaluated at each post-Baseline visit (Week 1, Week 6, or Month 3) in this study:

Table 3: Response Endpoints

Response Endpoint	Response criteria in mean diurnal IOP
IOP 20% response	Percent reduction from Baseline $\geq 20\%$
IOP 25% response	Percent reduction from Baseline $\geq 25\%$
IOP 30% response	Percent reduction from Baseline $\geq 30\%$
IOP ≤ 18 mmHg response	Mean diurnal IOP ≤ 18 mmHg

For a response endpoint, the response rate at a post-Baseline visit is calculated as the proportion of subjects who met the response criterion at the post-baseline visit.

4.4. Safety-Related Definitions

4.4.1. Adverse Event

Under Protocol 011710IN, an AE is defined as any untoward medical occurrence that occurs in a study subject, regardless of the causal relationship with the study treatment. An *on-study* AE can occur any time after the date of informed consent through the last study visit. An AE will be considered as *treatment-emergent* if the onset date of the AE occurred on or after the treatment start date till up to 2 days (twice the scheduled dosing interval) after treatment end date.

Treatment-emergent AEs (TEAEs) are a subset of on-study AEs. Both on-study and TEAEs will be collected, but only TEAEs will be tabulated.

The severity of each AE will be graded by the Clinical Investigator as Mild, Moderate, or Severe. AEs will also be rated by the Investigator as to their causality/relationship to the study drug.

Each AE will be classified into a system organ class (SOC) and coded to a preferred term (PT) using Medical Dictionary for Regulatory Activities (MedDRA), version 21.1 published in 2018.

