## 7. INVESTIGATIONAL PLAN

### 7.1. Overall Study Design

This is a Phase III, randomized, double-masked, active-controlled, parallel-group and multi-center study investigating the efficacy and safety of DE-117 Ophthalmic Solution 0.002% in subjects with glaucoma or OHT.

[figure not shown]
See the study design diagram in [Figure 1](#). This study will consist of a Screening Period of up to 35 days including a washout period of up to 28 days (+ 7 days window) and a 3-month Double-Masked Treatment Period.

Approximately 400 adult subjects and up to 30 pediatric subjects with glaucoma or OHT who meet all eligibility criteria will be randomized in a 1:1 ratio to receive either:

- DE-117 Ophthalmic Solution 0.002% QD (20:00) and Vehicle QD (08:00), or
- Timolol Maleate Ophthalmic Solution 0.5% BID (20:00 & 08:00).

In the Double-Masked Treatment Period, Timolol Maleate Ophthalmic Solution 0.5% will be used as active control.

**Figure 1:** Study Design

At the Screening visit (Visit 1), subjects will be screened against the inclusion and exclusion criteria. Eligible subjects will be instructed to discontinue use of all IOP-lowering medications, if any, during a washout period as follows (up to +7 days as a window is allowed):

- Miotics: 7 days
- Oral/topical Carbonic Anhydrase Inhibitors (CAIs): 7 days

- Alpha agonists: 14 days
- Alpha/beta agonists: 14 days
- Alpha antagonists ( $\alpha$ 1 blocker): 28 days
- Beta antagonists ( $\beta$  blocker, including  $\alpha\beta$  blockers): 28 days
- Prostaglandin Analogs (PGA): 28 days
- Rho kinase inhibitor: 28 days
- Combination drugs: The longest washout period of the individual component will be used.

During the required washout period, subjects who discontinue their current treatment may, if the Investigator deems it necessary, be treated with a short-acting IOP lowering agent, topical CAI, e.g., brinzolamide or dorzolamide eye drops, one drop twice daily. Topical CAI treatment must be stopped 1 week before the randomization at Visit 2 (Baseline, Day 1). An interim safety visit during the washout period (mid-washout visit; Visit 1a) may be performed during the washout period if, in the Investigator's opinion, a subject's IOP may be of concern during the washout period. If subjects are treated with a topical CAI during the washout period, mid-washout visit (Visit 1a) is recommended to be performed.

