#### **12.1.1.2. Reporting Adverse Events**

AEs, whether spontaneously reported by the subject or noted by authorized study personnel, will be recorded in the subject's medical record and on the appropriate AE electronic case report form (eCRF). Each recorded AE will be described by its duration (represented in dates), affected eye(s) (if applicable), maximum severity of the AE, seriousness criteria, suspected relationship to the study medication, actions taken with the study medication and the study participation, outcome of the AE, and any other attributable causes of the AE.

Regardless of relationship to the clinical study, AEs that occur at any time after the subject has provided written informed consent until subject withdrawal or the scheduled exit visit, must be recorded. To improve the quality and precision of acquired AE data, Investigators should observe the following guidelines:

- Whenever possible, use recognized medical terms when recording. Do not use colloquialisms and/or abbreviations.
- If known, record the diagnosis (i.e., disease or syndrome) rather than component signs and symptoms and /or laboratory or test findings (e.g., record congestive heart failure rather than dyspnea, rales, and cyanosis, and enlarged heart on chest x-ray). However, other events that are considered unrelated to an encountered syndrome or disease should be recorded as individual AEs (e.g., if congestive heart failure and severe headache are observed at the same time and are clinically unrelated, each event should be recorded as an individual AE).

- If the diagnosis is not known, then record the leading component sign, symptom or test finding and describe the other clinically related findings in the narrative description of the case. A suspected diagnosis can be used and described as such (e.g., record suspected or probable myocardial infarction); this has to be updated in the clinical database once the diagnosis is confirmed.

AEs occurring secondary to other events (e.g., sequelae) should be identified by the primary cause. A primary AE, if clearly identifiable, generally represents the most accurate clinical term. If a primary AE is recorded, events occurring secondary to the primary event should be described in the narrative description of the case. For example:

The subject developed orthostatic hypotension and subsequently fainted and fell to the floor wherein she experienced a head trauma and neck pain.

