The primary AE in this example is orthostatic hypotension. The fall, head trauma and neck pain should be described in the narrative description of the case.

- For intermittent events (e.g., intermittent headache), the event onset date should be recorded as the date the subject first started to experience the event and resolution date should reflect when the last occurrence resolved or stopped. Separate AEs for each event should not be recorded. For example, if a subject experienced headache on 14SEP2015 lasting for three hours, then subsequently experienced intermittent episodes of headache every day for approximately 3 hours until 21SEP2015, then the AE date of onset is 14SEP2015 and the resolution date is 21SEP2015.
- For intermittent events, record the maximum severity of the individual events. For example, if a subject complains of intermittent headaches for one week and the severity of each headache ranges from mild to moderate, then the severity would be moderate.
- For intermittent hospitalizations occurring for a primary AE (e.g., in a subject with multiple sclerosis, commonly known for its relapsing and remitting course, in some cases leading to multiple hospital confinements), the subsequent hospitalizations should be described in the narrative description of the case.
- If treatment was initiated, include the treatment and duration of the medication(s) in the eCRF.

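### Treatment-emergence is decided by onset date alone, so an AE that began before first dose and worsened on study drug goes untabulated whenever the worsening stays in the original record

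*SAP*

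**What the plan says.** SAP 4.4.1 makes an AE treatment-emergent "if the onset date of the AE occurred on or after the treatment start date till up to 2 days" after the treatment end date. The same section then states: "Both on-study and TEAEs will be collected, but only TEAEs will be tabulated". Under SAP 9.1, non-treatment-emergent AEs go into a listing.

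Protocol 12.1.1.2 starts collection well before dosing: "AEs that occur at any time after the subject has provided written informed consent until subject withdrawal or the scheduled exit visit, must be recorded". Protocol 7.1 describes a "Screening Period of up to 35 days including a washout period of up to 28 days", with a 7-day window on the washout.

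Protocol 12.1.1.2 also sets how each AE is recorded. The items captured once per AE include its dates and the "maximum severity of the AE, seriousness criteria", along with relationship and action taken with study drug. For intermittent events, "the event onset date should be recorded as the date the subject first started to experience the event", the highest severity of the episodes is entered, and "Separate AEs for each event should not be recorded".

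**The concern.** The SAP's classification rule and the protocol's recording rules each look reasonable alone. Together they leave a gap. A treatment-emergent definition normally has two limbs: events that start on treatment, and events already present that get worse on treatment. SAP 4.4.1 has only the first. The protocol's handling of intermittent events gives a complaint that began in washout a pre-dose onset date however it later evolves.

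The safety objective is a comparison of DE-117 with timolol, and the AE tables are its main display. Aggravation by study drug of a complaint already present at first dose is a drug effect that those tables should show. Any loss need not be equal in the two arms, since it would be larger in whichever arm aggravates such complaints more.

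**Working it through.** The SAP gives no figure to reproduce here. The check applies the rule to illustrative records and looks for any clause that would rescue the event.

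**Inputs**

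- Classification rule and restriction of tables to treatment-emergent AEs: SAP 4.4.1.
- Study day numbering, with treatment start as Study Day 1: SAP 4.1.4.
- Recording rules: Protocol 12.1.1 and 12.1.1.2.
- AE tables and listings: SAP 9.1. Disposition: SAP 7.1. Missing dates: SAP Table 5.

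**Rule applied to four records**

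1. Intermittent headache, mild, first felt on Study Day -10. It becomes severe on Day 30 and study drug is stopped. Protocol 12.1.1.2 directs one record: onset Day -10, severity Severe. Day -10 is before Day 1, so the AE is not treatment-emergent. It is absent from the AE, suspected-reaction and AE-leading-to-discontinuation tables, and from the SAE table if it became serious. It appears in listings. Under SAP 7.1 the drug discontinuation is still counted if AE is the main reason.
2. Continuous event with the same dates, kept by the site in its existing record. The result is the same, but here the protocol does not expressly direct a single record.
3. The same event, with the worsening entered by the site as a new AE dated Day 30. It is treatment-emergent and tabulated.
4. Onset date completely missing. SAP Table 5 treats the AE as treatment-emergent.

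Records 1 and 3 describe the same clinical course and are classified differently. Record 4, with no onset date at all, is counted, while record 1, with documented worsening on drug, is not.

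**Search for a rescuing clause**

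- Nothing in SAP 4.4.1, 6.2.3 or 9.1 brings in pre-dose-onset AEs that worsen.
- SAP 9.1.1 to 9.1.3 speak of AEs developed during the study, which read alone could include pre-dose events. The general restriction in 4.4.1 still governs tabulation.
- Protocol 14.8 plans tables of subjects with any AE, without a treatment-emergent restriction. SAP section 10, which lists departures from the protocol, does not mention the narrowing.

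**Length of the pre-dose period**

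For a subject with the full 35-day screening period who exits on the target Day 91, the pre-dose share of AE recording time is 35 / (35 + 91) = 35 / 126 = 28%. For a subject off IOP-lowering medication for the last 28 days, Protocol 7.1 asks for as little as 1 day: 1 / (1 + 91) = 1%. So 28% describes the longest screening period. It measures recording time only and says nothing about how many events worsen.

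**The case against.** A reader might infer that every AE that starts in washout and worsens on drug is missing from every table. The documents do not support that, for four reasons.

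- Protocol 12.1.1 treats any significant change after consent as an AE. A site may rely on this to enter the worsening as a new AE, which would then be counted. The bar on separate records is stated only for intermittent events, and its examples are short runs of headache. Protocol 12.1.1 does not, however, require a new record when an AE already recorded worsens, and for intermittent events 12.1.1.2 points the other way. The result therefore depends on site practice.
- The events are not lost. Non-treatment-emergent AEs and AEs leading to discontinuation are listed (SAP 9.1), and drug discontinuations are counted by main reason (SAP 7.1). Worsening from baseline on biomicroscopy, BCVA and vital signs is summarised separately (SAP 9.2, 9.3, 9.6). This stands and limits the harm. It does not restore the AE counts by arm, and symptoms such as headache or irritation may have no matching examination finding.
- Exclusion criteria are applied again at Visit 2, so some important washout events would prevent randomization. This stands and shrinks the pool.
- A reader might also infer a number of omitted subjects, or a direction of bias. The documents give neither the frequency of AEs present at first dose nor the proportion that worsen, so neither inference can be made.

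It is also tempting to say that the plan counts worsening of conditions present before consent but ignores worsening of those that began after it. Protocol 12.1.1 does not tie a pre-existing condition to the date of consent, so that contrast is not established.

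**Conclusion.** The point holds in conditional form. SAP 4.4.1 uses onset date as its only test and restricts tables to treatment-emergent AEs. Where worsening stays in the original record, as Protocol 12.1.1.2 directs for intermittent events, an AE that began between consent and first dose and worsened on drug is shown only in listings. Where a site opens a new record, it is tabulated. A stated rule can therefore give the wrong safety count.

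The size cannot be derived from the documents. The number is probably small, given the re-screening at Visit 2 and the need for both a pre-dose onset and later worsening, but that is a judgement. The point rests on the recording fields described in Protocol 12.1.1.2. If the eCRF also captures dated severity changes, the gap is easier to close than described here. It should be corrected because the repair is standard and cheap. It does not affect the efficacy analyses.

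**What to change.** Before unmasking, amend SAP 4.4.1 so that a treatment-emergent AE is either:

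- an AE with onset from first dose to 2 days after the treatment end date, or
- an AE with earlier onset that worsened within that period.

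The second limb cannot be programmed directly, because no date of worsening is described as collected. Apply it to pre-dose-onset AEs that meet at least one of these conditions, using fields Protocol 12.1.1.2 already requires:

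- rated Related to study drug, which for a pre-dose onset implies either a change after dosing or a data query;
- led to an action with study drug;
- became serious after first dose.

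Confirm timing from narratives or source while treatment is still masked, and document each decision. Record the change in SAP section 10, together with the restriction to treatment-emergent AEs, which differs from Protocol 14.8.

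Rewording Protocol 12.1.1.2 or the eCRF instructions would come largely too late: SAP 3.1 says enrollment was complete when the SAP was finalized.

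The cost is one SAP clause, a small masked review and a few more AEs counted. These conditions will still miss a worsening that was rated unrelated, stayed non-serious and led to no action with study drug. Such events remain in the listing.

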## 8.5. Subject Withdrawal Criteria

An early termination occurs when a subject who provides written informed consent ceases participation in the study, regardless of circumstances, before the completion of the study. Subjects may be voluntarily discontinued from study medication or withdrawn from the study at any time for any reason. In addition, the Principal Investigator or Medical Monitor may discontinue the study drug administration or terminate a subject's study participation due to any of the following reasons:

- AE (e.g., not compatible with study continuation)
- Non-compliance with study drug
- Lack of efficacy (e.g., IOP exceeds 34 mmHg in either eye after randomization)
- Progressive disease
- Protocol deviation (e.g., not fulfilling eligibility criteria)
- Pregnancy
- Voluntary withdrawal by subject at any time for any reason
- Lost to follow-up (e.g., no contact is possible)
- Death
- Other

If the study drug administration is discontinued prior to Visit 5, they should be encouraged to still participate in all follow-up study visits until Visit 5 on an observational basis.

[figure not shown]
If the study drug administration is discontinued prior to Visit 5, then to the extent possible, all procedures for Early Termination will be performed on the day of early drug discontinuation as per [Table 3](#) (for adult subjects) or [Table 4](#) (for pediatric subjects). Subjects who are discontinued from the study early will not be replaced.

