3.4. Visits and Assessments

There are 5 scheduled visits for each subject. Assessments at each visit and the time/visit window for each post-baseline assessment are specified in the Assessment Schedule for Adult ([Table 1](#)). If the study drug administration is discontinued prior to Visit 5, the subject should be encouraged to still participate in follow-up study visits until Visit 5 on an observational basis. For subjects whose study participation is terminated prior to Visit 5 (Month 3), to the extent possible, all assessments scheduled for Visit 5 (Month 3) will be performed at the Exit Visit.

Table 1: Assessment Schedule for ADULT Subjects

	Washout Period		Double-Masked Treatment Period			
	Visit 1 Screening	Washout Period (up to 4 weeks) Optional Visit 1a	Visit 2 Eligibility/Baseline (Day 1)	Visit 3 Week 1 (Day 8±2)	Visit 4 Week 6 (Day 43 ±3)	Visit 5 Month 3 (Day 91±7) Exit or Early Termination ⁿ
Informed Consent(s) including the optional consent for pharmacogenomics/ genomics laboratory research study ^a	X					
Inclusion/Exclusion Criteria	X		X			
Demographics and Medical History, including prior PGA ^b	X					
Concomitant Medications/ Therapies	X	X	X	X	X	X
Dosing Compliance				X	X	X
AEs		X	X	X	X	X
Pregnancy Test ^c	X		X			X
Vital Signs (blood pressure/pulse rate) ^d	X		X (08:00)			X (08:00)
Refraction ^e	X					
BCVA ^e	X	X	X (08:00)	X (08:00)	X (08:00)	X (08:00)
Biomicroscopy ^f	X	X	X (08:00)	X (08:00)	X (08:00)	X (08:00)
IOP ^g	X	X	08:00 10:00 16:00	08:00 10:00 16:00	08:00 10:00 16:00	08:00 10:00 16:00
Pachymetry ^h	X					
Instill study medication after IOP measurement				X (08:00)	X (08:00)	X (08:00)
Iris color, eyelash, eyelid ⁱ			X (photo)			X (photo)
Gonioscopy ^j	X					
Visual Field ^k	X					
Ophthalmoscopy ^l	X (pupil dilation)		X (16:00)			X (16:00, pupil dilation)
Blood Sampling for Pharmacogenomics/genomics ^m				X		

Table 1: Assessment Schedule for ADULT Subjects (Continued)

	Washout Period		Double-Masked Treatment Period			
	Visit 1 Screening	Washout Period (up to 4 weeks) Optional Visit 1a	Visit 2 Eligibility/Baseline (Day 1)	Visit 3 Week 1 (Day 8±2)	Visit 4 Week 6 (Day 43±3)	Visit 5 Month 3 (Day 91±7) Exit or Early Termination ⁿ
Dispense Study Medication			X		X	
Collect Study Medication					X	X
Phone call to remind subject to take evening dose on the day before each visit				X	X	X

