9.1.2. Macular Edema

Subjects who developed AEs during the study with one of the following preferred terms will be included in the macular edema summary:

- Macular edema
- Cystoid macular edema

Macular edema start time (in terms of study day) and duration of the AE will be summarized using mean, standard deviation, median, minimum, and maximum by study eye and fellow eye separately. To allow for the computation of simple descriptive statistics, only subjects who develop macular edema during the study will be used for the macular edema start time summary, and only subjects who develop these AEs during the study and later resolved will be used in the duration of AE analysis.

Change from baseline in BCVA at the onset of macular edema, when macular edema is resolved, and at the last visit will be summarized using mean, standard deviation, median, minimum, and maximum by study eye and fellow eye separately. Subjects with pseudophakic lens or phakic lens at baseline who developed macular edema during the study will be summarized by frequency and percentages separately.

The aforementioned summaries will be performed at the eye level. All macular edema AEs will be provided in a listing.

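### Adverse events that begin more than 2 days after the last dose reach only listings, and the SAP's special ocular summaries use a different, unreconciled event set

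*SAP*

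**What the plan says.** SAP 4.4.1 sets up two nested classes of event. An on-study "AE can occur any time after the date of informed consent through the last study visit". A treatment-emergent AE must have its onset on or after the treatment start date and "till up to 2 days (twice the scheduled dosing interval) after treatment end date". The section then limits the tables: "Both on-study and TEAEs will be collected, but only TEAEs will be tabulated". SAP 9.1 provides tables of AEs, SAEs, suspected reactions and ESIs, and says that non-treatment-emergent AEs and ESIs are listed.

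Observation does not stop with the drug. For subjects who discontinue study medication before Visit 5, protocol 8.5 says "they should be encouraged to still participate in all follow-up study visits until Visit 5 on an observational basis"; SAP 3.4 repeats this. Protocol 12.1.1.2 requires that "AEs that occur at any time after the subject has provided written informed consent until subject withdrawal or the scheduled exit visit, must be recorded". Protocol 8.5 also says that, to the extent possible, "all procedures for Early Termination will be performed on the day of early drug discontinuation".

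The special ocular summaries are worded differently. SAP 9.1.2 reads: "Subjects who developed AEs during the study with one of the following preferred terms will be included in the macular edema summary". Sections 9.1.1 (ocular inflammation) and 9.1.3 (cosmetic change) use the same construction, and none of the three mentions treatment emergence. Protocol 14.8 plans SOC/PT tables for subjects with any AE, again without a treatment-emergent limit. SAP section 10, which records additions and changes to the protocol's analyses, lists the full analysis set, a key secondary endpoint and the sensitivity analyses, but not this restriction.

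**The concern.** There are two linked problems.

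First, the plan collects AEs after drug discontinuation by design and then gives them no by-arm rate. A listing preserves each event but does not let a reader compare arms. This covers SAEs and ESIs as well as minor events.

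Second, the SAP applies two inclusion rules to the same kind of event and does not say which governs. Read as written, a macular edema or iritis that begins three weeks after the last dose enters the special summary in 9.1.1 or 9.1.2 but not the SOC/PT table, and for macular edema not the ESI table. Two programmers could reasonably report different counts for an ESI. Macular edema is the event for which this matters most: protocol 12.1.3 notes that it has been reported in DE-117 trials and requires cases to be followed to an outcome.

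**Working it through.** **The window.** SAP 4.4.1 gives 2 days as twice the dosing interval. For DE-117 once daily, 2 × 24 h = 2 days, which reproduces the figure. For timolol twice daily, 2 × 12 h = 1 day. The SAP applies 2 days to both arms, so the window itself does not differ by arm.

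**Excluded time per subject.** Untabulated days = Visit 5 day − (last-dose day + 2). Visit 5 is Day 91, range Day 84 to 98 (SAP Table 1).

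| Last dose | Visit 5 on Day 91 | Visit 5 on Day 84 to 98 |
|---|---|---|
| Day 8 | 91 − 10 = 81 | 74 to 88 |
| Day 43 | 91 − 45 = 46 | 39 to 53 |
| Day 61 | 91 − 63 = 28 | 21 to 35 |
| Day 90 or 91 (completer, Visit 5 on Day 91) | 0 | |

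**Excluded time per arm.** The documents give no expected discontinuation rate. Assume 5-10% of 200 per arm stop, stop days uniform on Day 1 to 91, and all stay to Day 91.

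- Mean excluded days per stopper = (91 − 2 − 1)² / (2 × 90) = 88² / 180 = 43.0.
- At 5%: 10 × 43.0 = 430 subject-days. At 10%: 20 × 43.0 = 860.
- Total per arm = 200 × 91 = 18,200. Shares: 430/18,200 = 2.4% and 860/18,200 = 4.7%.
- If only half of those who stop remain to Day 91 and the rest leave when drug stops, the shares halve to about 1.2% and 2.4%.

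**Effect of one event.** A subject whose only event is excluded lowers that arm's tabulated incidence by 1/200 = 0.5 percentage points.

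**The same event under each rule.** Take a macular edema with onset 21 days after last dose in a subject still attending:

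- SAP 4.4.1 with the SOC/PT and ESI tables of 9.1: not counted (21 > 2 days).
- SAP 9.1 listings: shown.
- SAP 9.1.2 as worded: counted, and by actual treatment under section 9.
- Protocol 14.8: counted.
- SAP 9.4 Month 3 retina/macula/choroid shift table: an abnormal finding is counted by treatment, because no cut-off after last dose is stated and SAP 4.1.5 selects the visit nearest Day 91.

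**The case against.** Restricting AE tables to treatment-emergent events is a defensible convention, because events that begin well after the last dose are harder to attribute to the randomized drug. Several safeguards also narrow the gap, and all of them stand:

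- Classification is by onset date. A reader might infer that events detected late are dropped, but an event found at Visit 5 and dated within the window is still tabulated, and SAP 6.2.3 treats an AE with a completely missing onset date as treatment-emergent.
- Early Termination procedures, including dilated ophthalmoscopy, are due on the day drug stops, to the extent possible. Many events already present would be found then.
- Excluded events are listed, and Month 3 fundus and lid/lash/iris findings stay in by-treatment examination tables (SAP 9.4, 9.5).
- Attendance after stopping is encouraged, not required, so the subject-day figures are upper bounds at the assumed rates.
- If 4.4.1 is meant to govern all of section 9.1, the special summaries and the AE tables agree. If 9.1.1 to 9.1.3 are meant literally, those ocular events do have a summary by arm. The omission and the inconsistency cannot both apply at full strength to the same ocular event.

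A reader might also infer that the arms will stop drug at different rates and that the AE comparison is therefore biased. The documents do not support that. SAP 8.1.2 mentions unequal discontinuation only as a condition that would trigger a trimmed-mean analysis.

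What the objection does not remove: off-drug AEs outside the special categories, SAEs included, have no by-arm rate; the wording of 4.4.1 and of 9.1.1 to 9.1.3 remains unreconciled; and the departure from protocol 14.8 is unrecorded.

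**Conclusion.** The point holds as a gap in reporting and an inconsistency of definition. It does not show that the safety comparison is biased. AEs, SAEs and ESIs with onset more than 2 days after the last dose, in subjects who stop early but keep attending, are left out of the by-arm AE tables, and the SAP's own rules can give two counts for the same macular edema or iritis. Completers lose nothing. The excluded time is at most about 2-5% of subject-days per arm, assuming 5-10% stop drug at evenly spread times and all stay to Day 91; it is less if some leave. Any difference between arms in this excluded time is possible but not established. The change is worth making because the data are already collected and the remedy is cheap.

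**What to change.** 1. Keep the treatment-emergent tables as planned.
2. Add one by-arm table of all AEs, ocular AEs, SAEs and ESIs with onset from first dose to last study visit, showing events that begin after the treatment-emergent window separately.
3. State in SAP 9.1 that the ocular inflammation, macular edema and cosmetic change summaries and the ESI table all use one named event set.
4. Record the treatment-emergent restriction in SAP section 10 as a change from protocol 14.8.

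The cost is SAP wording and one repeated table shell on data already collected. The downside is interpretive: every event the new table brings in has onset more than 2 days after the last dose, and some may be confounded by non-study IOP-lowering therapy. Showing those events separately keeps this visible.
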